### 6.7 Treatment of Adverse Events

Following are recommended guidelines for the management of AEs. Medications used to treat AEs must be recorded on the appropriate eCRF.

## 6.7.1 Treatment of Acute Rejection Episodes

In all suspected acute rejection episodes, regardless of initiation of anti-rejection treatment, a renal biopsy should be performed within 48 hours.

Acute rejections should be treated with bolus methylprednisolone (other CS are acceptable at an equivalent dose) according to local practice. Recommended treatment is at least 3 boluses of IV methylprednisolone with a minimal dose of 250 mg/bolus or at least 2 boluses of IV methylprednisolone with a minimal total dose of 750 mg.

Subjects who experience steroid-resistant rejections, vascular rejections, or rejections with a Banff grade  $\geq$  2B (Appendix 6Appendix 6Appendix 6Appendix 6Appendix 7) may be treated with other anti-rejection therapies (i.e., antibody therapy).

It is important to note that the combination of siplizumab and other T-cell depleting antibodies, e.g., ATG, alemtuzumab, mTOR inhibitors (sirolimus or everolimus), IVIG or costimulatory blockade (belatacept) have not been investigated and may result in overlapping pharmacology. In the setting of an acute rejection episode, the selection and use of one or more of these agents in combination with siplizumab is at the investigator's discretion based on their experience.

All episodes of acute rejection, and any medications used for suspected or confirmed acute rejections, must be entered on the corresponding eCRF, preferably within 24 hours.

## 6.7.2 Management of BK Viremia

BK Polyoma virus (BKV) screening generally utilizes plasma (or whole blood) viral load (VL) molecular assays. Urine studies (cytology for "decoy cells," BKV DNA or VP-1 mRNA) are less specific. Decoy cells are shed infected tubular and ureteric epithelial cells with an enlarged nucleus with a large basophilic intranuclear inclusion by urine cytology. Cytology cannot distinguish BKV from adenovirus and false negative tests also occur. A urinary test for BKV (cytology for decoy

cells or urine BKV loads over 7-log geq/mL) is adequate for screening; if negative, the risk for polyoma virus associated nephropathy (PVAN) is low.

Quantitative cutoffs for presumptive diagnosis of BKV nephropathy include plasma DNA VL >10.000 copies/mL (whole blood polymerase chain reaction (PCR) VL >1500–3500 copies/mL). urine VP1 mRNA load >6.5 X 10e5 copies/ng total RNA, or urine DNA load >10e7 copies/mL; higher viral loads are increasingly predictive of PVAN.

World Health Organization (WHO) standards will be utilized in the performance of BKV quantitative nucleic acid testing (ONAT) to ensure minimization of interlaboratory variability.

Biopsy is suggested for confirmation if creatinine is elevated. Renal histopathology provides definitive diagnosis of PVAN (Fishman 2017).

If a subject is found to have BK Viremia or PVAN, the event should be recorded in the appropriate eCRF as an AE or SAE, and they should be managed as per local center practice.

#### 6.7.3 Management of Delayed Graft Function (DGF)

DGF for this trial is defined as the need for dialysis performed within 7 days of transplant. However, in the event that a subject experiences DGF and does not undergo dialysis, DGF must still be reported as an AE in these subjects.

NOTE: Patients who require dialysis (up to two sessions), with the purpose of correcting electrolyte abnormalities in the immediate post-transplant time period, would not meet the definition of DGF for purposes of this study.

In case DGF is reported as an AE and dialysis is also reported, the end of DGF is considered the day the last dialysis session ends. For all other subjects it is when the renal dysfunction is considered resolved by the investigator.

In case a subject experiences DGF, the DGF is by definition starting at reperfusion after the transplantation procedure. If the graft dysfunction is starting later according to the Investigator, then this condition is considered secondary graft dysfunction.

In case of DGF, treatment will be according to local practice. DGF treatments must maintain sufficient immunological coverage for the graft and may include maintaining, interrupting, or reducing the dose of study treatment and the use of rATG. If a polyclonal antibody or rATG is used prior to Day 4, the investigational product must be discontinued, and the subject will be placed on SoC per local practice.

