ATG is a polyclonal mixture of chimeric (rabbit / human) immunoglobulins derived from the serum of rabbits inoculated with human thymocytes. The precise mechanisms underlying the therapeutic efficacy of ATG are not entirely known, although T-cell depletion plays a critical role. Quantitative analysis by Popow and colleagues demonstrated that ATG is largely comprised of T-cell specific antibodies to CD2 (7.5%), CD4 (1.2%) and CD8 (14.3%). In addition, a high proportion of antibodies to cell surface markers like CD11a/CD18 and CD45 that are broadly expressed on all leukocytes as well as antigens expressed on endothelial cells and cells of nonhematopoietic origin like CD98, CD99, CD147 and MHC class I (Popow et al 2013). This broad expression of pleiotropic antibodies has been linked to the exaggerated pharmacology and offtarget toxicities expected with ATG administration. In addition, both in vitro and in vivo studies have suggested a number of other possible ATG mechanisms, including lymphocyte surface antigen modulation and transcription factor activation. ATG may disrupt immune cell processes, such as cytokine production, chemotaxis, endocytosis, stimulation and proliferation, as well as leukocyte-endothelial cell adhesion. Finally, ATG may also promote cell death via the induction of apoptosis, antibody-dependent cell-mediated cytotoxicity (ADCC) and complement-mediated cytolysis (CDC) of various immune cells (Andress et al 2014) Considering the profound immunologic consequences of complete, long-term, lymphocyte depletion, polyclonal induction with ATG is not a benign therapy. The benefits of reduced acute rejection rates can come with the risks associated with over-immunosuppression and mechanism-based side effects. A course of ATG induction results in profound lymphocyte depletion for >12 months with slow recovery and inversion of CD4/CD8 populations that can take an additional 2-3 years to reach pre-transplant levels (Hardinger et al 2004). Mechanistic side effects such as infusion reactions, cytokine release syndrome, increased risk of infections and post-transplant lymphoproliferative disorder (PTLD) have also been reported with ATG administration.

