Although the ideal study would employ a double-blind, double-dummy methodology to minimize bias, in consideration of the inherent complexity of this study (multiple arms, frequent visits, siplizumab PD activity, interim assessment after each dose, the different dosing schedules of siplizumab and ATG and extensive investigations), it has been decided to utilize an open-label design. This open-label design will not only minimize the risks for subjects during the initial investigation of siplizumab should the need for rapid intervention arise, such as emergent SAEs, but also avoids the additional difficulties associated with placebo infusions in the control group. It is recognized that Investigator bias can affect the management of subjects receiving investigational

treatment; especially in an open-label study setting. In general, such scrutiny biases the study in favor of the control arm. As such, efforts to minimize bias for or against the siplizumab treatment arms will be managed through the use of a limited number of high-quality transplant centers with similar SoC and subject management.

Due to the unknown tolerability and PD activity, this study will enroll a moderate immunological risk de novo patient population who would typically be treated with ATG induction. This population was selected since they typically present a lower risk of post-transplant complications, including delayed graft function (DGF) and provide a fair assessment of clinical activity while not requiring the highest level of immunosuppression. While it is recommended per current KDIGO guidelines, that ALL renal transplant patients receive induction with anti-IL2R therapy (KDIGO 2009), due to the expected overlapping activity with siplizumab, inhibition of T-cell activation, anti-IL2R or other T-cell depleting induction (e.g., ATG) will not be allowed in combination with siplizumab in this trial. In the setting of acute rejection prophylaxis with induction or no induction in the planned study population, the risk of 'omitting' SoC induction is manageable. Without induction and SoC therapy (TAC, MMF and CS) 12-month BPAR rates of 12.4% and 13.3% for living and deceased donor allografts have been reported, respectively (Tanriover 2015). These rates (BPAR) are similar to those in patients treated with anti-IL2 induction of 11.7% and 12.4%, respectively in the same population (Tanriover 2016).

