#### 6.2.3 **Investigational Product Dosing Regimen**

The starting dose for siplizumab will be 0.2 mg/kg with escalation to 0.6 mg/kg.

The planned duration of investigational treatment is 5 days. Subjects will receive a total of two doses of siplizumab: pre- or intra-operatively on Day 0 and on Day 4. Subjects may be discontinued from treatment earlier at the discretion of the investigator or upon request of the subject.

Siplizumab dose adjustments and/or interruptions for a given subject are not permitted. The siplizumab infusion rate may be changed in the event of an infusion reaction.

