#### 6.2.8 **Dose Escalation Guidelines**

Before escalating to the next dose level, an interim review of all available safety/tolerability (e.g., AEs, SAEs, clinical laboratory assessments, vital signs), PD (immunophenotyping), receptor occupancy and PK data (if available) up to a minimum of approximately 28 days post dose for at least 4 siplizumab treated subjects in the lower dose arm will be performed.

ITB-MED Page 55 of 117 Confidential

This 28-day safety period allows sufficient time for subjects to reach full-receptor occupancy, maximum pharmacodynamic activity and for the presentation of acute, drug related, toxicities.

For treatment cohorts where receptor occupancy at the 28-day assessment cut-off is >99% in at least 2 subjects, dose escalation decisions will be deferred by a minimum of approximately 14 days until results of the next PD assessment have been analyzed and reviewed. If the CD2 receptor occupancy remains at >99% in at least 2 subjects at the second assessment time point, reevaluation of receptor occupancy on an approximately 14-day schedule may continue until a decision to escalate has occurred or stopping criteria have been satisfied.

Where siplizumab concentrations are not quantifiable, i.e., with low doses, rapid clearance or assay limits, receptor occupancy or lymphocyte recovery will serve as the only measure of investigational treatment exposure for dose escalation decisions.

In order to escalate to the next dose level, the data at the aforementioned review must be assessed as satisfactory or not clinically significant. The decision to escalate to the subsequent dose cohort will be made jointly between ITB-MED and the Investigator(s) following a review of all relevant safety and PK/PD data.

To assure subjects are not exposed to a prolonged duration of T-cell depletion and/or sustained receptor occupancy and consequent immunomodulation / immunodepletion, the selection of the next highest dose will be guided by the following criteria:

Escalation will not proceed if the dose is not considered safe, regardless of the duration of target suppression or PD activity

Siplizumab dose escalation will be stopped when:

- 1. An average of  $\geq$  24 weeks (168 days) duration of T-cell depletion has been measured (defined as <10% of baseline (i.e., 90% depletion) in ≥2 subjects or
- 2. An average of  $\geq$  24 weeks (168 days) duration of  $\geq$  99% peripheral CD2 receptor occupancy has been measured in ≥2 subjects or

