#### 6.9 Prohibited Treatment

Immunosuppressants and induction treatment other than those specified in the protocol are NOT allowed after informed consent up to the end of study. If the use of any of these medications or other non-protocol immunosuppressants is discovered prior to randomization/enrollment, the subject must not be randomized and will be recorded as a screen failure. If discovered after randomization/enrollment, no further doses are to be given, and the subject should continue on the randomized/assigned treatment regimen, noting the protocol deviation.

The exception is for the treatment of acute rejection not responding to corticosteroids.

The use of concomitant medications that may influence tacrolimus levels should be avoided, please refer to Appendix 6 and local prescribing information.

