### **7.4. PD Analysis Set**

The PD Analysis Set will include all subjects in the Full Analysis set with available PD data and no protocol deviations with relevant impact on PD data.

For all analysis sets, subjects will be analyzed according to the study treatment(s) received.

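### Section 6.7.3 allows rATG for delayed graft function in siplizumab subjects although Section 4 rules the combination out, and no rule says how such a subject is handled in the escalation count or the siplizumab PD summaries

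*Protocol*

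**What the plan says.** **On rATG in siplizumab subjects.** Protocol Section 4 states that "anti-IL2R or other T-cell depleting induction (e.g., ATG) will not be allowed in combination with siplizumab in this trial". Section 6.9 prohibits immunosuppressants and induction agents that the protocol does not specify, and adds: "The exception is for the treatment of acute rejection not responding to corticosteroids". Section 6.7.1 is broader. It also allows antibody therapy for vascular rejection or Banff 2B and above without first requiring steroid failure, and it notes that siplizumab with other depleting antibodies is untested. Section 6.7.3 says DGF treatment "may include maintaining, interrupting, or reducing the dose of study treatment and the use of rATG", and continues: "If a polyclonal antibody or rATG is used prior to Day 4, the investigational product must be discontinued". It says nothing about rATG on Day 4 or later.

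**On dose changes.** Section 6.2.3: "Siplizumab dose adjustments and/or interruptions for a given subject are not permitted". Section 6.2.6 bars dose adjustments other than for body weight.

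**On the escalation review.** Section 6.2.8 says that a review "for at least 4 siplizumab treated subjects in the lower dose arm will be performed". Sections 3.1, 4.4 and 12.8 count in the same way, and none requires both doses or the absence of rATG. Section 9.3 lets a non-evaluable subject be made up by new enrollment until at least four evaluable subjects are available, and sends the reader to the escalation guidelines for the numbers. Those guidelines do not use the term.

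**On the analysis sets.** In both documents one dose of the assigned drug fixes the treatment received. SAP 7.4 admits subjects with PD data and "no protocol deviations with relevant impact on PD data". SAP 11.1 summarizes immunophenotyping in the safety population by treatment.

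**The concern.** The comparator can reach the test arm under one section while another says that it will not. The plan does not say what then happens to the data.

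Two uses of the data are exposed:

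- **Escalation review.** It is meant to show 28-day safety, occupancy and depletion on a two-dose regimen. A subject given one dose and then rATG shows neither the full exposure nor siplizumab's effect alone. Section 6.2.8 adds that where siplizumab cannot be quantified, occupancy or lymphocyte recovery is the only exposure measure for escalation.
- **Secondary PD objective.** This is the time course of siplizumab-induced depletion and recovery. On rATG the protocol says: "A course of ATG induction results in profound lymphocyte depletion for >12 months". After a switch, that depletion would be averaged into the siplizumab arm and reported as siplizumab's.

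**Working it through.** The documents state no power or calculated sample size, so there is no planned figure to reproduce. The check is mainly textual, with illustrative arithmetic.

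**1. The clinical passages side by side**

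| Situation in a siplizumab subject | Section 4 | Section 6.9 | Sections 6.7.1 and 6.7.3 |
|---|---|---|---|
| rATG for DGF before Day 4 | ATG not allowed with siplizumab | DGF is not the named exception | Allowed; investigational product stopped |
| rATG for DGF on Day 4 or later | Same | Same | Allowed; no further rule |
| Antibody for vascular or Banff 2B+ rejection without steroid failure | Speaks of induction only | Outside the named exception | Allowed |

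The interrupting-or-reducing wording of 6.7.3 conflicts with 6.2.3 only if study treatment there includes siplizumab.

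**2. Does stopping the second dose avoid overlap?** Fraction of the first dose remaining = 0.5^(t / half-life).

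- Half-life 8.5 days (Protocol 1.1.4.5): 92%, 85% and 78% at Days 1, 2 and 3.
- Half-life 14 to 49 hours (Protocol 1.1.4.6, at 0.06 and 0.12 mg/kg): 31–71%, 9–51% and 3–36%.

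Some overlap remains in either case.

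**3. Does any rule exclude the switched subject from the four?** The subject is siplizumab-treated on the ordinary meaning of the words. The Safety Set rule keeps the subject in the siplizumab arm. Section 3.1 replaces only subjects not transplanted or not given a first dose. Section 9.3 could remove the subject as non-evaluable, but the term has no definition. The 28-day clock starts at the last investigational product dose, which for this subject is Day 0.

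**4. Where do the later data go?** If rATG under 6.7.3 is a permitted treatment, it is no deviation, and the PD Set exclusion does not operate. SAP 11.1 uses the safety population in any case. SAP 7.3, 7.4, 10.2.2 and 11.1 to 11.3 contain no rule for values after non-randomized rATG.

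**5. Size.** One subject is 1/4 = 25% of the minimum review set and 1/8 = 12.5% of an arm. Let q be the probability that a siplizumab subject is switched. It is an assumption, because the documents give no rate.

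P(at least 1 of 4) = 1 − (1 − q)^4; P(at least 2 of 4) = 1 − (1 − q)^4 − 4q(1 − q)^3.

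| q | At least 1 of 4 | At least 2 of 4 |
|---|---|---|
| 2% | 7.8% | 0.2% |
| 5% | 18.5% | 1.4% |
| 10% | 34.4% | 5.2% |
| 20% | 59.0% | 18.1% |

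With no events, the one-sided 95% upper bound on an event rate is 1 − 0.05^(1/n). It is 52.7% for four fully exposed subjects and 63.2% for three.

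**The case against.** **Section 4 speaks of induction, and 6.7.3 of managing an adverse event.** That is a fair distinction, and 6.7.3 does stop siplizumab if rATG comes before Day 4. It softens the conflict without removing it: the first dose has been given, and rATG from Day 4 is not addressed.

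**Section 6.9 bars only what the protocol does not specify, and 6.7.3 specifies rATG.** This reading is available. It weakens the conflict with 6.9 but strengthens the data point, because rATG for DGF is then no deviation and the subject stays in the PD Set. The opposite reading also has support, since 6.9 needed an explicit exception for rejection therapy that 6.7.1 already specifies.

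**Study treatment may mean the background drugs.** Sections 6.4 and 6.8 use similar terms that way, so the conflict with 6.2.3 is conditional.

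**Stronger readings that a reader might infer:**

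- *That a switched subject does count toward the four.* No passage says so. Section 9.3 offers a way out, and escalation is a joint judgment on all the data, not a mechanical count.
- *That rATG would help to clear escalation.* Under 6.2.8, prolonged depletion or occupancy in two subjects defers or stops escalation, so rATG depletion would tend to hold it back. The 24-week criterion cannot be observed in a subject only 28 days after dosing.
- *That the 7.5% anti-CD2 content of rATG would read as siplizumab occupancy.* The protocol describes a distinct siplizumab epitope and leaves the assay as free or total CD2. No interference is documented.

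**The risk is small and the step is past.** Section 4 says the population was chosen for lower risk, including of DGF, and Section 5.2 excludes donors after cardiac death. Deceased-donor kidneys with cold ischemia below 30 hours remain eligible. SAP 5.1 reports the interim analysis as done, so escalation has very probably been decided. The SAP gap remains.

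**Conclusion.** The point holds as a gap in the rules. Sections 4 and 6.7.3 do not agree on rATG in siplizumab subjects, Sections 6.7.1 and 6.9 differ on antibody rescue, and nothing expressly excludes a switched subject from the four. The documents do not show that such a subject was or must be counted, or that escalation was wrongly cleared.

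The consequence that stands most firmly is in the analysis. Under the plan as written, lymphocyte values after rATG remain in the siplizumab summaries and would lengthen the apparent depletion and delay the apparent recovery. One subject carries 12.5% of an arm of 8. How often this would arise is unknown; the 8% to 59% for at least one among four rests wholly on the assumed 2% to 20%, taken as independent between subjects. The upper end has no support in the documents.

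**What to change.** 1. **Protocol.** Reconcile Sections 4, 6.2.3, 6.2.6, 6.7.1, 6.7.3 and 6.9, including the period from Day 4 onward and whether study treatment in 6.7.3 includes siplizumab. Which clinical rule applies is for the sponsor and investigators.
2. **Evaluability.** Have the sponsor define evaluable in 6.2.8 and 9.3, stating how a subject given rATG or another non-randomized depleting antibody is treated in the count of four. All safety data are reviewed regardless. If escalation has already taken place, the clinical study report should say whether any of the four was such a subject.
3. **SAP 7.3, 7.4, 10.2.2 and 11.1 to 11.3.** Flag PK, CD2 occupancy and lymphocyte values obtained after the first non-randomized depleting antibody. Leave them out of the siplizumab depletion and recovery summaries and the PK/PD summaries, whether or not the use is classed as a deviation. Keep listing them, state how many subjects and values are affected, and keep the subject in the safety and FAS analyses.

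The cost is wording plus slightly fewer PD observations in an arm of 8. Cohort size is unchanged. The SAP rule should be fixed before database lock.

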#### **Primary Graft Non-Function (PGNF)** 6.7.4

PGNF is defined as dialysis starting after transplantation with a continuous record of post-transplant dialysis until either transplantectomy, re-transplantation or death. PGNF should be reported on the Graft Loss eCRF.

If a subject is placed on permanent dialysis (or re-transplanted), the Graft Loss and AE eCRFs should be completed, and an SAE of graft loss reported.

## 6.7.5 Management of EBV-PTLD

EBV-PTLD is a serious disease. Transplant clinicians managing suspected and confirmed PTLD should follow local institutional guidance on the diagnosis and management of EBV-PTLD, including consulting with transplant infectious disease and hematology-oncology clinicians where relevant.

In patients diagnosed with EBV-PLTD, therapy must be individualized. rATG and siplizumab doses planned for this trial are expected to result in T- and NK-cell depletion and minimal to no modulation of the B-cell compartment, respectively. Clinicians should refer to the siplizumab IB or local labelling for rATG when considering therapeutic options for the treatment of EBV-PTLD.

Consensus guidelines on the diagnosis and management of EBV-LPD and PTLD in the setting of solid organ transplantation have been published and may be referenced (Allen and Preiksaitis 2013 and Parker et al 2010).

